**NOTES :**

- Please refer to Appendix 11: List of Data Displays which details the population to be used for each displays being generated.

**4.1. Protocol Deviations**

- Important protocol deviations (including deviations related to study inclusion/exclusion criteria, conduct of the trial, patient management or patient assessment) will be summarised and listed.
- Protocol deviations will be tracked by the study team throughout the conduct of the study in accordance with the Protocol Deviation Management Plan.
  - Data will be reviewed prior to unblinding and freezing the database to ensure all important deviations and deviations which may lead to exclusion from the analysis are captured and categorised on the protocol deviations dataset.
  - This dataset will be the basis for the summaries and listings of protocol deviations.
- A separate summary and listing of all inclusion/exclusion criteria deviations will also be provided. This summary will be based on data as recorded on the inclusion/exclusion page of the eCRF.

## 5. CONSIDERATIONS FOR DATA ANALYSES AND DATA HANDLING CONVENTIONS

Table 1 provides an overview of appendices within the RAP for outlining general considerations for data analyses and data handling conventions.

**Table 1 Overview of Appendices**

Section	Component
10.1	Appendix 1: Time & Events
10.2	Appendix 2: Treatment States and Phases
10.3	Appendix 3: Data Display Standards & Handling Conventions
10.4	Appendix 4: Derived and Transformed Data
10.5	Appendix 5: Premature Withdrawals & Handling of Missing Data
10.6	Appendix 6: Values of Potential Clinical Importance
10.6	Appendix 7: DMID Adult Toxicity Tables for Adverse Event Assessment
10.8	Appendix 8: Multiple Comparisons & Multiplicity
10.9	Appendix 9: Model Checking and Diagnostics for Statistical Analyses.
10.10	Appendix 10: Abbreviations & Trade Marks.
10.11	Appendix 11: List of Data Displays.

## 6. STUDY POPULATION ANALYSES

### 6.1. Overview of Planned Analyses

The study population analyses will be based on the Safety population, unless otherwise specified.

Table 2 provides an overview of the planned study population analyses, with full details of data displays being presented in Appendix 11: List of Data Displays.

**Table 2 Overview of Planned Study Population Analyses**

Display Type	Data Displays Generated		
	Table	Figure	Listing
Randomisation			
Randomisation			Y
Subject Disposition			
Subject Disposition	Y		Y
Reason for Screening Failures	Y		Y
Reason for Withdrawals	Y		Y
Inclusion and Exclusion Criteria Deviations			Y
Demography			
Demographic Characteristics	Y		Y
Medical Conditions and Concomitant Medications			
Concomitant Medication	Y		Y
Medical Conditions (Current/Past)	Y		Y

**NOTES :**

Y = Yes display generated.

## 7. PRIMARY STATISTICAL ANALYSES

### 7.1. Safety Analyses

#### 7.1.1. Overview of Planned Safety Analyses

The safety analyses will be based on the Safety population, unless otherwise specified.

Table 3 provides an overview of the planned Safety analyses, with full details of data displays being presented in Appendix 11: List of Data Displays.

**Table 3 Overview of Planned Safety Analyses**

Display Type	Absolute				Change from Baseline			
	Summary		Individual		Summary		Individual	
	T	F	F	L	T	F	F	L
Exposure								
Extent of Exposure	Y			Y				
Adverse Events								
All AEs	Y			Y				
All Drug-Related AEs	Y			Y				
Serious AEs				Y				
Withdrawal AEs				Y				
Laboratory Values								
Clinical Chemistry	Y			Y	Y			
Hematology	Y			Y	Y			
Urinalysis (Dipstick)	Y			Y				
ECGs								
ECG Findings	Y			Y				
ECG Values	Y			Y	Y			
Vital Signs								
Vital Signs	Y			Y	Y			
Cardiac Telemetry								
Cardiac Telemetry				Y				
Liver								
Liver Events [1]				Y				
Cardiovascular								
Cardiovascular Events [1]				Y				
Injection Site Reactions								
Injection Site Reaction Events [1]				Y				
Rash								
Rash Events [1]				Y				
Biomarker								
Cytokines			Y	Y				

---

**NOTES :**

1. Conditional displays, they will only be produced when an event has occurred.
  - T = Table, F = Figure, L = Listing, Y = Yes display generated.
  - Summary = Represents TFL related to any summaries (i.e. descriptive statistics) of the observed raw data.
  - Individual = Represents TFL related to any displays of individual subject observed raw data.

## 8. SECONDARY STATISTICAL ANALYSES

### 8.1. Pharmacokinetic Analyses

#### 8.1.1. Overview of Planned Pharmacokinetic Analyses

The pharmacokinetic (PK) analyses will be based on the PK population, unless otherwise specified.

Table 4 provides an overview of the planned PK analyses, with further details of data displays being presented in Appendix 11: List of Data Displays.

**Table 4 Overview of Planned Pharmacokinetic Analyses**

Endpoint / Display Type	Untransformed							Log-Transformed						
	Stats Analysis			Summary		Individual		Stats Analysis			Summary		Individual	
	T	F	L	T	F	F	L	T	F	L	T	F	F	L
PK Plasma Concentrations				Y	Y  [2]	Y 	Y							
PK Urine Concentrations							Y							
PK Plasma Parameters	Y			Y		Y	Y	Y			Y			
PK Urine Parameters				Y		Y	Y							

**NOTES :**

- T = Table, F = Figure, L = Listings, Y = Display generated.
- Stats Analysis = Represents TFL related to any formal statistical analyses (i.e. modelling) conducted.
- Summary = Represents TFL related to any summaries (i.e. descriptive statistics) of the observed raw data.
- Individual = Represents FL related to any displays of individual subject observed raw data.

 Linear and Semi-Log plots will be created on the same display.

 Separate mean, median, and median trough (Part 2 only) concentration plots will be generated.

#### 8.1.2. Drug Concentration Measures

Refer to Appendix 3: Data Display Standards & Handling Conventions (Section 10.3.3 Reporting Process & Standards).

#### 8.1.3. Pharmacokinetic Parameters

##### 8.1.3.1. Deriving Pharmacokinetic Parameters

- Refer to Appendix 3: Data Display Standards & Handling Conventions (Section 10.3.3 Reporting Process & Standards).
- The pharmacokinetic parameters will be calculated by standard non-compartmental analysis according to current working practices and using Phoenix WinNonlin Version 6.2.1 or higher.

- All calculations of non-compartmental parameters will be based on actual sampling times.
- Pharmacokinetic parameters described in Table 5 will be determined from the plasma GSK3342830 concentration-time data, as data permits.
- Pharmacokinetic parameters described in Table 6 will be determined from the urinary GSK3342830 concentration data, as data permits.

**Table 5 Derived Plasma Pharmacokinetic Parameters**

Parameter	Parameter Description
C max	Maximum plasma concentration
T max	Time to C max
AUC(0-t)	AUC from time zero to the last quantifiable concentration after dosing
AUC(0-∞)	AUC extrapolated from time 0 to infinity (estimated for single dose in Part 1 and Part 3 and on Day 1 for repeat dose in Part 2)
AUC(0-τ)	AUC over the dosing interval τ
t 1/2	Terminal elimination half-life
CL	Total systemic clearance
V ss	Steady-state volume of distribution
C τ	Trough concentration
Ratio of invariance	Time invariance ratio, calculated by (AUC(0-τ) on Day 15)/(AUC(0-∞) on Day 1)
Ratio of accumulation	Accumulation ratio, calculated by (AUC(0-τ) on Day 15)/(AUC(0-τ) on Day 1)

**NOTES:**

- Additional parameters may be included as required.

**Table 6 Derived Urinary Pharmacokinetic Parameters**

Parameter	Parameter Description
Feu(t 1 -t 2 )	Urinary excretion ratio relative to dose
CL r	Renal clearance
A e	Amount excreted in urine

**8.1.3.2. Statistical Analysis of Pharmacokinetic Parameters**

The following pharmacokinetic statistical analyses will only be performed, if sufficient data is available (i.e. if subjects have well defined plasma profiles).

Pharmacokinetic Statistical Analyses
Assessment

 
• Dose proportionality of GSK3342830.
 

Pharmacokinetic Statistical Analyses
Endpoint(s)

 
An estimate of slope (with corresponding 90% CI).
 

Model Specification

 
Dose proportionality of AUC(0-∞) and Cmax on Day 1 after single dose (Part 1) and for repeat dose groups (Day 15 in Part 2), AUC(0-τ) and Cmax of GSK3342830 on Day 15 will be assessed separately by day using the following power model:  <math display="block">y = \alpha * \text{dose}^\beta</math> 
where y denotes the PK parameter being analyzed and α depends on the random error in the repeat dose phase where subjects take the study drug in a parallel-group fashion. Dose proportionality implies that β=1 and will be assessed by estimating β along with its 90% CI. The exponent, β, in the power model will be estimated by regressing the loge-transformed PK parameter on loge-transformed dose.
 <math display="block">\log(y) = \log(\alpha) + \beta * \log(\text{dose})</math> 
The power model will be fitted by restricted maximum likelihood (REML) using Statistical Analysis Software (SAS) Proc Mixed, with a fixed effect term for dose. The PK parameter endpoint and the factor dose will be loge-transformed prior to the analysis.
 
 
In the case where dose proportionality is not established over the entire dosing range, secondary analysis of dose proportionality will be assessed for select doses over the higher dosing range with the power model or by pair-wise analysis of variance (ANOVA) using the SAS mixed models procedure. If the secondary analysis using the pair-wise ANOVA approach is performed, a reference dose would be chosen based on the lowest clinically relevant dose over which the pharmacokinetics can be adequately described and the other doses would be treated as test doses.
 

Model Checking & Diagnostics

 
Refer to Appendix 9: Model Checking and Diagnostics for Statistical Analyses.
 

Model Results Presentation

 
An estimate of slope (with corresponding 90% CI) will be provided as a measure of potential dose proportionality (i.e. a slope of approximately 1 implies dose proportionality) will be produced in tabular format.
 

Assessment

 
Time invariance of GSK3342830.
 

Endpoint(s)

 
An estimate of time invariance ratio (with corresponding 90% CI).
 

Model Specification

For the repeat dose cohorts (Part 2), the time invariance ratio will be assessed by fitting a mixed effect model for AUC(0-∞) on Day 1 and AUC(0-τ) on Day 15 data with subject as a random effect and group (group=1 for AUC(0-∞) on Day 1, and group=2 for AUC(0-τ) on Day 15) as a fixed effect for each cohort.

Model Checking & Diagnostics

 
Refer to Appendix 9: Model Checking and Diagnostics for Statistical Analyses.
 

Model Results Presentation

 
The time invariance ratio of GSK3342830 will be estimated by calculating the ratio of the geometric least squares means of group 1 (AUC(0-τ) on Day 15) to group 2 (AUC(0-∞) on Day 1) and the corresponding 90% CI for each cohort.
 

Assessment

Pharmacokinetic Statistical Analyses

 
Accumulation ratio of GSK3342830.
 

Endpoint(s)

 
An estimate of accumulation ratio (with corresponding 90% CI).
 

Model Specification

 
For the repeat dose cohorts (Part 2), the accumulation ratio (<math>R_0</math>) will be calculated as the ratio of <math>AUC(0-\tau)</math> on Day 15 to <math>AUC(0-\tau)</math> on Day 1 for each subject. The dosing interval (<math>\tau</math>) will be equal to 8 hours. Following log-transformation, <math>AUC(0-\tau)</math> of GSK3342830 on Days 1 and 15 will be analyzed by a mixed effect model, fitting dose, day, and dose-by-day interaction as fixed effects and subject as a random effect. For each dose, point estimate and 90% CI for the difference "<math>AUC(0-\tau)</math> on Day 15 - <math>AUC(0-\tau)</math> on Day 1" will be constructed using the appropriate error term. The point estimate and associated 90% CI will then be exponentially back-transformed to provide point and 90% CI estimates for the ratios "<math>AUC(0-\tau)</math> on Day 15: <math>AUC(0-\tau)</math> on Day 1." If dose-by-day interaction is not significant, then a single point estimate and 90% CI pooled across all doses for the ratio <math>AUC(0-\tau)</math> on Day 15: <math>AUC(0-\tau)</math> on Day 1 may be constructed with all estimates for each dose.
 

Model Checking & Diagnostics

 
Refer to Appendix 9: Model Checking and Diagnostics for Statistical Analyses.
 

Model Results Presentation

 
The point estimate and 90% CI for the accumulation ratios of <math>AUC(0-\tau)</math> on Day 15 to <math>AUC(0-\tau)</math> on Day 1 will be calculated.
 

Assessment

 
Steady state assessment of GSK3342830.
 

Endpoint(s)

 
An estimate of the slope (with corresponding 90% CI).
 

Model Specification

 
To evaluate whether steady state was achieved, statistical analysis of steady-state <math>C_\tau</math> will be performed after log-transformation of <math>C_\tau</math> on Days 3, 6, 9, 12, 13, and 15. A mixed effect model will be fitted by dose and day (as a continuous covariate) as a fixed effect term and subject as a random effect term. Distributional assumptions underlying the statistical analyses will be assessed by visual inspection of residual plots. Normality will be examined by normal probability plots, while homogeneity of variance will be assessed by plotting the residuals against the predicted values for the model. Alternative analyses of the data will be performed if any of the model assumptions appear to be violated.
 

Model Checking & Diagnostics

 
Refer to Appendix 9: Model Checking and Diagnostics for Statistical Analyses.
 

Model Results Presentation

 
The coefficients for the slope of the day effect on the log-scale will be used to evaluate steady-state for each dose group. Using the pooled estimate of variance, the 90% CIs for the slope will be calculated.
 

Model Results Presentation

 
The least squares geometric mean ratio and 90% CI for the comparison of <math>AUC(0-t)</math>, <math>AUC(0-\infty)</math> and <math>C_{max}</math> from Japanese subjects (Part 3) to subjects of non-Japanese heritage of the same dose level (Part 1) will be calculated.
 

Assessment

 
Assessment of GSK3342830 PK in healthy adult Japanese subjects vs the same dose level of
 

Pharmacokinetic Statistical Analyses
healthy adult subjects in Part 1.
Endpoint(s)

• The geometric mean ratio and associated 90% CI for Part 3 vs Part 1.

Model Specification

• To evaluate whether there is a difference in the PK parameters in healthy adult Japanese subjects, a fixed effect model will be fitted with Study Part as fixed effect.

Model Checking & Diagnostics

• Refer to Appendix 9: Model Checking and Diagnostics for Statistical Analyses.

Model Results Presentation


• The geometric mean ratio and associated 90% CI will be presented in a table.

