
 
To investigate the safety and tolerability of GSK3342830 after administration of repeat IV doses in healthy adult subjects
 
	
 
Clinical safety data from AEs, clinical laboratory tests, vital signs (blood pressure, heart rate, temperature, and respiration rate), and 12-lead ECG readings
 

Secondary Objectives	Secondary Endpoints

 
To determine the pharmacokinetics of GSK3342830 after administration of repeat IV doses in healthy adult subjects
 
	
 
Plasma and urine concentrations and PK endpoints include AUC(0-t) and AUC(0-∞) on Day 1 only, AUC(0-τ), Cmax, Tmax, CL, Vss, t1/2, Cτ, Feu(t1- t2), Ae, and CLr of GSK3342830, as data permit
 

 
To assess dose proportionality of GSK3342830 after administration of repeat IV doses in healthy adult subjects
 
	
 
Pharmacokinetic endpoints include AUC(0-τ) and Cmax of GSK3342830 after administration of repeat IV doses for the assessment of dose proportionality, as data permit
 

Objectives	Endpoints

 
To examine the extent of accumulation, time invariance, and achievement of steady-state of GSK3342830 after administration of repeat IV doses in healthy adult subjects
 
	
 
Observed accumulation ratio (Ro) based on AUC and Cmax of GSK3342830 after administration of repeat IV doses, as data permit
 
Steady-state ratio (Rss) of GSK3342830 to assess time invariance, as data permit
 
Trough plasma concentrations at the end of the dosing interval (Cτ) to assess the achievement of steady-state of GSK3342830 after administration of repeat IV doses, as data permit
 

Exploratory Objectives	Exploratory Endpoints

 
To correlate PK parameters (AUC[0-t], AUC[0-∞], AUC[0-τ], and Cmax) of GSK3342830 with safety findings in healthy adult subjects after administration of repeat IV doses
 
	
 
Exposure-response analyses, as data permit
 

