Summary of Statistical Analysis of GSK3342830 Plasma Time Invariance in Part 2

Dose: XX mg

Parameter (Unit)	Day	N	Geometric LS Means	Regimen Comparison	Ratio of Geometric LS Means (%)	90% Confidence Interval of Ratio (%)	CVw(%)
AUC(0-inf) (Unit)	1	xx	x.xxx	15/1	x.xxx	(x.xxx, x.xxx)	x.xxx
AUC(0-tau) (Unit)	15	xx	x.xxx				

*Notes to programmer: Repeat for each dose level.*

Note: A linear mixed-effect model with group (group=1 for AUC(0-inf) on Day 1, and group=2 for AUC(0-tau) on Day 15) as a fixed effect and subject as a random effect was fitted to the natural log transformed PK parameters.

Source Data: Listing 46.

GlaxoSmithKline

Example : PK\_T1  
Protocol : 204847  
Population : PK Parameter

Page 1 of n

Table 3.12  
Summary of Statistical Analysis of GSK3342830 Plasma Accumulation Ratio in Part 2

Parameter (Unit)	Dose* (mg)	Day	N	Geometric LS Means	Regimen Comparison	Ratio of Geometric LS Means (%)	90% Confidence Interval of Ratio (%)	CVw(%)
AUC(0-tau) (Unit)	xx	1	xx	x.xxx	15/1	x.xxx	(x.xxx, x.xxx)	x.xxx
		15	xx	x.xxx				
	yy	1	xx	x.xxx	15/1	x.xxx	(x.xxx, x.xxx)	
		15	xx	x.xxx				
	zz	1	xx	x.xxx	15/1	x.xxx	(x.xxx, x.xxx)	
		15	xx	x.xxx				

Note: A linear mixed-effect model with dose, day, and dose-by-day interaction as fixed effects and subject as a random effect was fitted to the natural log transformed PK parameters.

\* If dose-by-day interaction is significant (p-value less than 0.05), then point estimate and 90% CI will be reported for each dose level.

Source Data: Listing 46.

GlaxoSmithKline

Example : PK\_T1  
Protocol : 204847  
Population : PK Parameter

Page 1 of n

Table 3.13  
Summary of Statistical Analysis of GSK3342830 Plasma Steady State Assessment in Part 2

Parameter	Days Included	Estimated Slope for Day	90% CI Lower-Upper
Ctrough (units)	3, 6, 9, 12, 13, 15	x.xxx	x.xxxx-x.xxxx

Note to programmer: If the 90% CI does not include zero, repeat the analysis without the data for the earliest day used in the previous analysis. Display the results for all models run.

Note: A mixed effect model will be fitted by dose and day (as a continuous covariate) as a fixed effect term and subject as a random effect term. No formal statistical hypothesis tested. Steady state is estimated to be achieved by the earliest day included in the analysis when the 90% CI of the slope includes 0.

Source Data: Table 3.06.

GlaxoSmithKline

Example : PK\_T2  
Protocol : 204847  
Population : PK Parameter

Page 1 of n

Table 3.14  

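### The steady-state model names no dose-by-day term, so it gives one slope for all doses, although the SAP promises a conclusion for each dose group

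*SAP*

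**What the plan says.** SAP 8.1.3.2, steady state assessment, log-transforms the trough "on Days 3, 6, 9, 12, 13, and 15" and specifies: "A mixed effect model will be fitted by dose and day (as a continuous covariate) as a fixed effect term", with subject as the random effect. Protocol 9.4.2 has the same model. Under results presentation the SAP says: "The coefficients for the slope of the day effect on the log-scale will be used to evaluate steady-state for each dose group", and then: "Using the pooled estimate of variance, the 90% CIs for the slope will be calculated".

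The Table 3.13 shell has a single row with one slope for day and one 90% CI. It has no dose column and no instruction to repeat by dose. Its programming note says that if the interval excludes zero, the earliest day is dropped and the model refitted. Its footnote gives the decision rule: "Steady state is estimated to be achieved by the earliest day included in the analysis when the 90% CI of the slope includes 0".

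The neighbouring repeat-dose analyses do carry dose. Time invariance is fitted for each cohort, and Table 3.11 is repeated by dose level. The accumulation model is specified as "fitting dose, day, and dose-by-day interaction as fixed effects and subject as a random effect", and Table 3.12 has a dose column.

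On accumulation, SAP 2.2 lists the endpoint "Observed accumulation ratio (Ro) based on AUC and Cmax of GSK3342830 after administration of repeat IV doses, as data permit". Table 5, the model in 8.1.3.2 and Table 3.12 use AUC(0-τ) only, and SAP 2.1 declares no change from the protocol.

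**The concern.** A model with main effects for dose and day has one day coefficient. It cannot give a slope for each dose group, which is what the text promises. Reading the model as a separate fit per dose would give such slopes, but it sits badly with listing dose as a fixed effect and with a pooled variance. A dose-by-day interaction gives both. A programmer who follows the model statement and the shell will produce one slope.

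Achievement of steady state is a stated Part 2 secondary objective, and the shell attaches a rule to that one interval. If the interval covers 0, every dose is declared at steady state from Day 3. If it excludes 0, early days are dropped for every dose. Drift at one dose can therefore be averaged away or attributed to doses that are flat, and opposite drifts cancel. Drift at the top dose matters most: the protocol's Appendix 9 predicts a median AUC(0-24) of 3078 h·µg/mL at 4000 mg TID, against a NOAEL exposure of 2875.

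**Working it through.** The documents give no precision or power figure for this analysis, so there is none to reproduce.

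**Inputs from the documents.** Trough days 3, 6, 9, 12, 13 and 15 (SAP 8.1.3.2). Three planned Part 2 cohorts with about 8 active subjects each (protocol 4.3). 90% CI.

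**Assumed, not in the documents.** Within-subject log-SD σ of 0.15 to 0.30, drift at the top dose only, a random intercept only, and complete data.

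**Spread of the days.** The days sum to 58 and their squares to 664. Sxx = 664 − 58²/6 = 103.33 per subject.

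**Slopes.** With balanced data, the common slope from the additive model is the mean of the three dose slopes. A slope b at one dose and 0 at the other two appears as b/3.

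**Standard errors at σ = 0.20.**
- One dose: 0.20/√(8 × 103.33) = 0.00696
- Common slope: 0.20/√(24 × 103.33) = 0.00402

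**Chance that the 90% CI lies above 0, with b = 0.02 per day.** Over 12 days this is a rise of exp(0.24) − 1 = 27%, and the common slope is 0.00667.
- Top-dose slope: 1 − Φ(1.645 − 0.02/0.00696) = 0.89
- Common slope: 1 − Φ(1.645 − 0.00667/0.00402) = 0.51

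The same formulas give 0.99 and 0.72 at σ = 0.15, and 0.61 and 0.30 at σ = 0.30.

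**Second calculation.** This one uses t quantiles, sets σ = √ln(1 + CV²), and lets the unmodelled slope differences inflate the additive model's residual variance. It gives the chance that the 90% CI includes 0 on the full set of days, so that steady state is declared from Day 3:

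| Within-subject CV (assumed) | Top-dose rise, Day 3 to 15 | Common slope | Top-dose slope |
|---|---|---|---|
| 20% | 20% | 66% | 29% |
| 20% | 30% | 45% | 7% |
| 20% | 50% | 14% | <1% |
| 30% | 20% | 78% | 56% |
| 30% | 30% | 67% | 31% |
| 30% | 50% | 42% | 5% |
| 40% | 20% | 83% | 69% |
| 40% | 30% | 76% | 51% |
| 40% | 50% | 59% | 19% |

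A 30% rise at the top dose appears in the common slope as exp(ln(1.3)/3) − 1, about 9%. Simulation with 4,000 trials per scenario agrees: at CV 30% and a 30% rise, the interval includes 0 in 67% of trials for the common slope and 32% for the top-dose slope. With no drift, both include 0 in about 90%.

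**Opposite drifts.** Slopes of +0.02, 0 and −0.02 give a common slope of 0.

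**The case against.** The wording is ambiguous. Plural coefficients and intervals, a conclusion per dose group and a pooled variance can together be read as dose-specific slopes from one joint fit, with the interaction simply left unnamed. Shells are also not always a reliable guide: Table 3.09 shows a dose column for a power-model slope fitted across doses. That reading is fair to the results paragraph. It does not rescue the model statement, which names no such term, or Table 3.13, which has nowhere to put per-dose results.

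The drift is hypothetical. With the protocol's predicted clearance of 0.82 to 0.93 mL/min/kg and volume of 0.121 L/kg (section 4.5), the one-compartment half-life is 0.693 × 121/0.93 = 90 min to 0.693 × 121/0.82 = 102 min, about 1.5 to 1.7 h against an 8-hour interval. Slow accumulation is therefore unlikely, and a 12-day rise would mean that clearance changes with time. This stands, although the protocol's simulation used a three-compartment model, so a slower phase is not excluded.

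The stakes are limited. Table 3.13 is an end-of-study output, no formal hypothesis is tested, and dose escalation does not use this slope. Figure 3.05 (median trough by day, all cohorts), Listing 42, the accumulation and time-invariance estimates and the residual checks offer partial cover. All of that stands, but none of these supplies the promised slope per dose.

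The Cmax omission is a separate matter and adds no weight to the slope argument. It is included because it concerns the same section and is corrected in the same edit.

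**Conclusion.** The concern holds. As written, the model and its shell give one steady-state verdict for all doses, while the text promises one for each. Under the assumptions shown, the chance of flagging a 2% per day drift confined to the top dose falls from 0.89 to 0.51 at log-SD 0.20. Across the SDs tried, the top-dose slope ranges from 0.61 to 0.99 and the common slope from 0.30 to 0.72.

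The dilution to one third and the √3 loss in signal-to-SE need only equal cohorts and complete data; the probabilities depend on the assumed SD and drift. Large drift with low variability would usually still be flagged: for a 50% rise at CV 20%, the common interval includes 0 in only 14% of trials. This is a secondary estimation problem that should be corrected; it does not threaten the primary safety objective. The missing Cmax accumulation ratio is a plain gap between endpoint and analysis.

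**What to change.** In SAP 8.1.3.2, fit log(Cτ) with dose (categorical), day (continuous) and dose-by-day as fixed effects and subject as random. Report the slope and 90% CI for each dose from that model. Add a dose column to Table 3.13 and apply the drop-earliest-day rule by dose. In the same edit, run the accumulation model on Cmax as well as AUC(0-τ) and add Cmax to Table 3.12.

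The cost is SAP wording, one model term and two shell changes; no new data are needed. The downside is precision: when all doses behave alike, a per-dose slope has an SE √3 ≈ 1.7 times that of the common slope. Nor does the interaction make an interval that covers 0 into proof of steady state. At CV 30% and a 30% rise, the top-dose interval still includes 0 in 31% of trials, so the size of each slope and its interval should be read alongside the rule.
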